4.5 Washout Period (Office Visit 3)

Office Visit 3 will occur within 7 days after PSG 2. In addition to PSG review, medications will be reviewed again to ensure stability of the PD medication regimen and absence of any prohibited medications. Any possible adverse events (AEs) will be assessed. General physical exam will be performed, including vital signs (blood pressure, heart rate, and respiratory rate).

PD symptoms and signs will be assessed with the complete MDS-UPDRS. Study scales (MoCA, ISI, ESS, BDI, BAI, CGI-C, SGI-C, C-SSRS) will be administered. Data from the wearable

sleep monitor will be collected. Laboratory testing will be performed as deemed appropriate by the investigator.

A new supply of study pills will be dispensed. For the washout period, all subjects will be given the placebo matching the dose being administered most recently (i.e. in the second half of treatment period 1).

4.6 Treatment Period 2

4.6.1 Office Visit 4

Office Visit 4 will occur 2 weeks (11-18 days) after Office Visit 3 and will mark the beginning of treatment period 2. Medications will be reviewed again to ensure stability of the PD medication regimen and absence of any prohibited medications. Any possible adverse events (AEs) will be assessed.

To serve as baseline scores for treatment period 2, PD symptoms and signs will be assessed with the complete MDS-UPDRS and study scales (MoCA, ISI, ESS, BDI, BAI, CGI-C, SGI-C) will be administered. Data from the wearable sleep monitor will be collected. Laboratory testing, including urine hCG, will be performed as deemed appropriate by the investigator.

A new supply of study pills will be dispensed in a crossover fashion. All subjects who received study drug in treatment period 1 will be given placebo in treatment period 2, and all subjects who received placebo in treatment period 1 will be given study drug in treatment period 2. For treatment period 2, double-blinding will be resumed. Initial dose for all subjects will be 10 mg qhs.

4.6.2 Phone Visit 4

Phone Visit 4 will occur 3-4 days after Office Visit 4 to review safety and tolerability through questioning about adverse events.

4.6.3 Phone Visit 5: Titration in Treatment Period 2

Phone Visit 5 will occur 2 weeks (12-15 days) after Office Visit 4 to review safety and tolerability through questioning about adverse events. The SGIC and C-SSRS will also be administered over the phone. Those subjects who report no AEs on suvorexant 10 mg po QHS (or matched placebo) and who report a persistent sleep disturbance will be titrated to suvorexant 15 mg po QHS (or matched placebo).

4.6.4 Phone Visit 6

Only for those subjects who are titrated to 15 mg, Phone Visit 6 will occur 3-4 days after Phone Visit 5 to review safety and tolerability through questioning about adverse events. For those who remain on 10 mg, Phone Visit 6 will not be conducted.

4.6.5 PSG 3

PSG 3 will occur 4 weeks (25-32 days) after Office Visit 4 and will mark the last night of Treatment Period 2. Subjects will continue to take the study medication on the night of PSG 3. This will be performed at EvergreenHealth's sleep lab according to their standard clinical protocol. At a minimum, PSG interpretation will report latency to persistent sleep (LPS), wakefulness after sleep onset (WASO), and sleep efficiency.

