1.5 Study Overview

The proposed study is a randomized, double-blind, placebo-controlled, cross-over trial to assess the safety, tolerability, and efficacy of suvorexant specifically in a cohort of 20 PD patients between the ages of 30 and 80 (inclusive) who have a complaint of insomnia. After informed consent is given, potential subjects will be screened to ensure they meet eligibility criteria. This will include an overnight polysomnogram (PSG), which will serve both as a baseline and a screening PSG. Active drug will be suvorexant 10 mg po QHS with an optional up-titration to 15 mg po QHS after 2 weeks. The first treatment period will be 4 weeks long, in which subjects will be randomized 1:1 to receive active drug or matching placebo. At the end of treatment period 1, subjects will undergo efficacy assessment with repeat PSG and clinical scales. This will be followed by a 2-week washout period with placebo; this period only will be single-blinded, as subjects only will be blinded to treatment. Subjects will then be crossed over into the alternate treatment group, which will once again be double-blinded; those on active treatment for period 1 will be switched to placebo, and those on placebo in period 1 will be switched to active treatment. Treatment period 2 will also be 4 weeks long, and at the end of this, subjects will undergo final assessment with PSG and clinical scales.

All subjects, whether in placebo or active arm, will receive a wearable sleep monitor to be worn continuously throughout the study. The subjects will be allowed to keep the wearable sleep monitor in lieu of a monetary reimbursement for Office Visit 1; subjects will receive a small monetary reimbursement per visit for each office visit after Office Visit 1.

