4.7 Final Visit (Office Visit 5)

Office Visit 5 will occur within 7 days after PSG 3. Medications will be reviewed again to ensure stability of the PD medication regimen and absence of any prohibited medications. Any possible adverse events (AEs) will be assessed. General physical exam will be performed, including vital signs (blood pressure, heart rate, and respiratory rate).

PD symptoms and signs will be assessed with the MDS-UPDRS and study scales (MoCA, ISI, ESS, BDI, BAI, CGI-C, SGI-C, C-SSRS) will be administered. Data from the wearable sleep monitor will be collected. Laboratory studies will be performed (CBC, CMP). Pregnancy testing with urine hCG will be performed if deemed appropriate by the investigator.

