- **Possibly related:** The suspected AE may or may not follow a reasonable temporal sequence from study treatment administration but seems to be the type of reaction that cannot be dismissed as unlikely. The event could have been produced or mimicked by the patient's clinical state or other therapy administered to the patient.
- **Probably related:** The suspected AE follows a reasonable temporal sequence from study treatment administration, abates upon discontinuation of the treatment, and cannot be reasonably explained by the known characteristics of the patient's clinical state or other treatments.
- **Definitely related:** The suspected AE follows a reasonable temporal sequence from study treatment administration, abates upon discontinuation of the treatment, and, if appropriate, resumes upon re-introduction of the treatment. Additionally, the suspected AE cannot be reasonably explained by the known characteristics of the patient's clinical state or other treatments.

The principal investigator and all other research staff except the research pharmacist will be blinded towards randomization of active drug versus placebo until after completion of study.

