7.3 Efficacy Assessment Based on Clinical Rating Scales

7.3.1 Insomnia Severity Index

The ISI is a 7-question survey assessing symptoms of insomnia. Maximum score is 28, with higher scores indicating greater severity. The ISI has been validated for use in insomnia research (Bastien 2001). This will be performed at Office Visits 2, 3, 4, and 5, and will be a secondary outcome measure.

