7.3.3 Subject's Global Impression of Change

The SGIC will be assessed by asking a single question at Phone Visits 2 and 5 and Office Visits 3, 4, and 5: "Since baseline (when first starting this study), how have your sleep symptoms changed?" Answers will be on a 7-point scale: 1 = much improved; 2 = somewhat improved; 3 = minimally improved; 4 = no change; 5 = minimally worse; 6 = somewhat worse; and 7 = much worse. This will be performed at Phone Visits 2 and 5 and at Office Visits 3, 4, and 5, and will be a secondary outcome measure.

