7.3.4 Clinician's Global Impression of Change

The CGIC will be assessed by the investigator at Office Visits 3, 4, and 5 using a similar question: "Since baseline (when first starting this study), how have the subject's sleep symptoms changed?" Answers will be on a 7-point scale: 1 = much improved; 2 = somewhat improved; 3 = minimally improved; 4 = no change; 5 = minimally worse; 6 = somewhat worse; and 7 = much

worse. This will be performed at Office Visits 3, 4, and 5, and will be a secondary outcome measure.

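### Nothing keeps the PSG 2 efficacy result from the investigator before CGI-C is scored at Office Visit 3, so that rating may be coloured by the primary endpoint

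*Combined protocol and SAP*

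**What the plan says.** Section 4.5 schedules Office Visit 3 within 7 days of PSG 2 and includes the sleep study among the visit's activities: "In addition to PSG review, medications will be reviewed again to ensure stability". The same section then lists the ratings: "Study scales (MoCA, ISI, ESS, BDI, BAI, CGI-C, SGI-C, C-SSRS) will be administered". The full MDS-UPDRS is also done at that visit.

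Section 7.3.4 names the rater for one of these scales: "The CGIC will be assessed by the investigator at Office Visits 3, 4, and 5 using a similar question". That question asks about change since the start of the study. Section 7.3.3 puts a matching question to the subject.

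Section 4.4.5 sets the minimum content of the PSG 2 report: LPS, WASO and sleep efficiency. Sections 1.10.1 and 7.2.1 make sleep efficiency the primary outcome. Section 4.3.2 has PSG 1 used to confirm eligibility, so a baseline for comparison is already at the site.

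On blinding, section 7.1.4 states: "The principal investigator and all other research staff except the research pharmacist will be blinded towards randomization". Sections 4.4.1 and 6.2 likewise protect the allocation code. None of these sections mentions access to PSG results.

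**The concern.** A global impression of change is useful beside a PSG endpoint because it shows, from a different source, whether a laboratory benefit can be seen clinically. The primary hypothesis (sections 1.6.1 and 3.3) relies on both kinds of evidence. If the rater has read the on-treatment sleep efficiency before scoring, part of any agreement between CGI-C and PSG may come from the report and not from the patient. This needs no guess about treatment.

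A second route runs through the crossover. Treatment in period 2 is the reverse of period 1, so an impression formed from PSG 2 about period 1 is also an impression about period 2. It could then touch the CGI-C at Office Visits 4 and 5, and the severity and relatedness grading that section 7.1.4 gives to the principal investigator.

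**Working it through.** The plan states no figure on this point, and section 8.2 gives no effect size, SD or power, so there is nothing to reproduce. The main check sets the sections side by side.

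1. **Same visit.** Section 4.5 puts the PSG review and CGI-C at Office Visit 3.
2. **Content.** AHI is a required item for PSG 1 (section 4.3.2) but not for PSG 2 (section 4.4.5). The three required items of the PSG 2 report are all efficacy outcomes.
3. **Who reviews.** Section 4.5 does not say. Appendix 11.1 assigns analysis of the recording to a sleep specialist as a separate item. A further review at an office visit is most naturally the investigator's, but this is an inference.
4. **Order and masking.** No section says that scales come first, that values are withheld, or that CGI-C has a separate rater.
5. **Need for the values.** Titration in period 2 (section 4.6.3) rests on what the subject reports. Washout dispensing (section 6.1) depends on the dose taken at the end of period 1. The withdrawal criteria named in section 5.4 do not mention PSG results. No stated decision uses the PSG 2 efficacy values.
6. **Carry-forward.** CGI-C at Office Visits 4 and 5 refers back to the same baseline, and section 4.6.1 reverses the treatments.

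One illustration shows how strong a clue to allocation the PSG could be. It rests on an assumption that the documents do not supply: d is the standardized active-minus-placebo difference in the change from PSG 1 to PSG 2, normally distributed, with 1:1 allocation and a guesser who knows the midpoint between the two mean changes. The chance of a correct guess is then Φ(d/2), and the expected number correct among 20 subjects is 20 × Φ(d/2).

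| Assumed d | Φ(d/2) | Expected correct of 20 |
|---|---|---|
| 0 | 0.50 | 10.0 |
| 0.2 | 0.54 | 10.8 |
| 0.5 | 0.60 | 12.0 |
| 0.8 | 0.66 | 13.1 |
| 1.0 | 0.69 | 13.8 |
| 1.5 | 0.77 | 15.5 |

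At d = 0.5 this is two more correct guesses than chance (12.0 − 10.0). Because the periods are linked, it is one guess per subject, not two. The 0.50 reference is also generous to the concern: staff already see symptom reports, adverse events, titration status and wearable data, so the increment due to the PSG is likely to be smaller. The table does not measure bias in CGI-C, which the documents do not allow to be computed.

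**The case against.** The strongest reply is that section 4.5 names no reviewer, content or sequence, and that the order of sentences in a paragraph is not an order of procedures. That is correct. The point therefore rests on what the plan permits and not on a stated breach. It still stands, because nothing in the plan prevents the exposure.

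A reader might infer more than the documents support:

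- **That the blind is broken.** The allocation code stays with the research pharmacist, and one PSG change is an imperfect clue. Section 1.5 does say of the washout that "this period only will be single-blinded, as subjects only will be blinded to treatment", but that is a declared feature with no PSG attached and is a separate matter.
- **That SGI-C, ISI and MDS-UPDRS question 1.7 are contaminated.** SGI-C is the subject's own answer ("The SGIC will be assessed by asking a single question at Phone Visits 2 and 5 and Office Visits 3, 4, and 5") and ISI is a symptom survey ("The ISI is a 7-question survey assessing symptoms of insomnia"). The PSG reaches them only if the subject is told the result, and no section says so. Subjects also wear a monitor that calculates sleep efficiency (section 4.3.1), which is a different channel.
- **That period 1 ratings are PSG-informed and period 2 ratings are not.** Section 4.7 lists no PSG review ("Office Visit 5 will occur within 7 days after PSG 3. Medications will be reviewed again"), but this rests on the absence of a phrase. Appendix 11.1, as it can be read, marks its PSG rows alike for Office Visits 3 and 5.
- **That titration at Phone Visit 5 is steered.** The rule uses the subject's report and gives the investigator's guess no stated role.
- **That the primary result is at risk.** Sleep efficiency comes from the recording, and section 8.5 ties superiority to it alone.

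It is also fair to say that CGI-C is one of eleven secondary rating-scale measures in an exploratory pilot. That limits the weight of the point without removing it.

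**Conclusion.** The point holds for CGI-C at Office Visit 3. The plan allows the investigator to know the primary endpoint value when scoring it, and no stated purpose requires this. The rating is then weaker as independent support for a PSG benefit. As a risk only, the same knowledge could carry into CGI-C at Office Visits 4 and 5 and into adverse event grading in period 2.

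This rests on two things: that the investigator performs the review, and that the report is open before the scale is scored. Neither is stated, and neither is excluded. The size of any bias in CGI-C is unknown. The PSG primary endpoint is not shown to be affected. This is an avoidable weakness in a secondary measure that is cheap to remove.

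**What to change.** Remove the PSG review from Office Visit 3. State in sections 4.5 and 4.7 that sleep efficiency, WASO and LPS from PSG 2 and PSG 3 go from the sleep center directly to the data file. They should be withheld from raters and from the subject at least until that subject's last rating at Office Visit 5, with only safety findings released to the site.

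If some review has to stay, say who performs it and require CGI-C, SGI-C, ISI, ESS and MDS-UPDRS to be completed before the report is opened, at both Office Visits 3 and 5. This is weaker: it protects the Visit 3 ratings, but knowledge of PSG 2 can still reach those at Visits 4 and 5. A CGI-C rater without access to PSG results is another option.

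The cost is a sentence in each of the two sections and an instruction to the sleep center. The drawback is that PSG 2 efficacy values cannot be discussed with the subject during the study. Feedback from the wearable monitor would remain and is not addressed by this change.

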4.7 Final Visit (Office Visit 5)

Office Visit 5 will occur within 7 days after PSG 3. Medications will be reviewed again to ensure stability of the PD medication regimen and absence of any prohibited medications. Any possible adverse events (AEs) will be assessed. General physical exam will be performed, including vital signs (blood pressure, heart rate, and respiratory rate).

PD symptoms and signs will be assessed with the MDS-UPDRS and study scales (MoCA, ISI, ESS, BDI, BAI, CGI-C, SGI-C, C-SSRS) will be administered. Data from the wearable sleep monitor will be collected. Laboratory studies will be performed (CBC, CMP). Pregnancy testing with urine hCG will be performed if deemed appropriate by the investigator.

4.8 Unscheduled Visits

Subjects may return to the clinic for safety evaluation or to receive additional study medication as needed. Unscheduled visits will include a review of concomitant medications and any adverse effects, and, if needed in the estimation of the study physician, physical examination in whole or in part.

5. STUDY POPULATION

The population for this study is PD patients aged 30-80 years old (inclusive) with symptoms of insomnia who meet all of the inclusion criteria (section 5.1) and who do not meet any of the exclusion criteria (section 5.2).

5.1 Inclusion Criteria

An eligible subject:

- Has signed and dated an IRB-approved informed consent form before any protocol-specific screening procedures are performed;
- Has a diagnosis of Parkinson disease according to the United Kingdom Parkinson Disease Society Brain Bank Criteria (UKBB);
- Has a modified Hoehn and Yahr (mHY) Stage of 1-3, inclusive;
- Is aged 30-80 years old, inclusive;
- Has had no change in PD medications during the 4 weeks preceding screening, with no dose changes during the study, except that PRN (as needed) doses of carbidopa/levodopa will be allowed to address periodic worsening of parkinsonian symptoms;
- Is willing and able to complete PSG;
- Is willing and able to abstain from alcohol, caffeine, and marijuana for 6 hours prior to and during each study-related PSG;
- Is willing and able to abstain from products containing nicotine during each study-related PSG;
- Has Insomnia Disorder defined by diagnostic criteria published in the Diagnostic and Statistical Manual of Mental Disorders, 5th edition (DSM-5); namely, subject report of all of the following:
 - One of the following: difficulty initiating sleep; difficulty maintaining sleep; or early morning waking;
 - Sleep disturbance causes clinically significant distress or impairment in social, occupational, educational, academic, behavioral, or other important areas of functioning;
 - Sleep difficulty has occurred on 3 or more nights per week;
 - Sleep difficulty has been present for at least the past 3 months;
 - Sleep difficulty occurs despite adequate opportunity for sleep;
 - Insomnia is not explained by another sleep disorder;
 - Insomnia is not attributable to physiological effects of a consumed substance;
- On screening PSG, has a latency to persistent sleep \geq 20 minutes OR total wakefulness after sleep onset \geq 45 minutes;
- May use other medications that could influence sleep, other than those specifically prohibited, as long as the dose is stable for 4 weeks preceding screening, with no dose changes during the study; and

- Has valid health insurance coverage at the time of study enrollment and expects this coverage to remain valid for the duration of the study period.

5.2 Exclusion Criteria

A subject will be excluded from the study if he or she meets any of the following:

- Is a woman who is breast-feeding, pregnant, or has the potential to become pregnant during the course of the study (fertile and unwilling/unable to use effective contraceptive measures);
- Has an implanted deep brain stimulator;
- Has a history of narcolepsy;
- Has a diagnosis of severe COPD, defined by $FEV1 < 50\%$ of predicted on most recent available pulmonary function test (PFT) (a PFT is not required if the subject has never been diagnosed with COPD);
- Has a history of severe obstructive sleep apnea (OSA) or evidence of severe OSA on screening PSG, with severe OSA defined as having an apnea-hypopnea index (AHI) > 30 ;
- Is concurrently using other CNS depressants, including alcohol, except that one alcoholic drink per day will be allowed for those with normal hepatic function provided the drink is consumed at least 2 hours prior to or 8 hours after taking the study drug, and no alcohol will be permitted for 6 hours before PSG visits;
- Is concurrently using digoxin;
- Is concurrently using any moderate or strong inhibitor of CYP3A;
- Is concurrently using any strong inducer of CYP3A;
- Has evidence at screening of severe hepatic impairment as defined by a Child-Pugh score > 10 ;
- Has evidence at screening of severe cognitive impairment as defined by a MoCA score < 15 , or has cognitive impairment that in the opinion of the investigator would prevent completion of study procedures or the ability to provide informed consent.
- Has evidence at screening of suicidal ideation in the past 6 months as defined by a positive response to any one of Questions 2-5 on the Columbia Suicide Severity Rating Scale (C-SSRS); or of a lifetime history of suicidal behavior as defined by any positive response to the suicidal behavior section of the C-SSRS.

5.2.1 Note on the Use of the Wearable Sleep Monitor

Of note, inability or unwillingness to use the WSM is specifically *not* an exclusion criterion. Those subjects who are unable or unwilling to use the WSM correctly will be allowed in the study (provided all eligibility criteria are otherwise met), and the observations from their WSM variables will be treated as missing data.

5.3 Prohibited Medications

The following medications are not permitted to be used within 14 days prior to screening nor for the duration of the subject's participation in the study:

- Digoxin;
- CNS depressants such as:
 - Benzodiazepines
 - Alprazolam
 - Chlorazepate
 - Chlordiazepoxide
 - Clonazepam
 - Diazepam
 - Estazolam
 - Flurazepam
 - Halazepam
 - Lorazepam
 - Midazolam
 - Oxazepam
 - Prazepam
 - Temazepam
 - Triazolam
 - Barbiturates
 - Amobarbital
 - Mephobarbital
 - Pentobarbital
 - Phenobarbital
 - Primidone
 - Secobarbital
 - Sodium thiopental
 - Opiates
 - Codeine
 - Hydrocodone
 - Hydromorphone
 - Methadone
 - Morphine
 - Oxycodone
 - Zolpidem
 - Zaleplon
 - Eszopiclone
- Moderate or strong inhibitors of CYP3A, such as:
 - Aprepitant
 - Atazanavir
 - Bromocriptine

- Chloramphenicol
- Ciprofloxacin
- Clarithromycin
- Cobicistat
- Conivaptan
- Darunavir
- Desipramine
- Diltiazem
- Dronedarone
- Erythromycin
- Felodipine
- Fluconazole
- Fluvoxamine
- Fosamprenavir
- Grapefruit Juice
- Imatinib
- Indinavir
- Itraconazole
- Ketoconazole
- Lopinavir
- Nefazadone
- Nelfinavir
- Nicardipine
- Posaconazole
- Quinidine
- Quinupristin
- Ritonavir
- Saquinavir
- Telaprevir
- Telithromycin
- Verapamil
- Voriconazole
- Strong inducers of CYP3A, such as:
 - Carbamazepine
 - Dexamethasone
 - Phenobarbital
 - Primidone
 - Phenytoin
 - Rifampin
 - St. John's Wort

